8.2 Adverse Event Reporting

We do not anticipate hazardous situations for the subjects as a result of this protocol. However, standard of care procedures will be in place for verification of correct radiopharmaceutical dose and route of administration. The study Principal Investigator (PI) or his designee will report all serious adverse events (per 21CFR§312.32) to the Stanford CCTO Safety Coordinator within 10 working days of becoming aware of the event (5 days if the event is life-threatening or results in death) using the Adverse Events Communication Form. If the Principal Investigator determines the unanticipated adverse device effect presents an unreasonable risk to subjects, the study will be terminated as soon as possible, but no later than 5 working days after the PI makes the determination, and no later than 15 working days after first receiving notification of the effect.

9. REGULATORY CONSIDERATIONS

9.1 Institutional Review of Protocol

The protocol, the proposed informed consent and all forms of participant information related to the study (eg, advertisements used to recruit participants) will be reviewed and approved by the Stanford IRB. Any changes made to the protocol will be submitted as a modification and will be approved by the IRB prior to implementation. The Protocol Director will disseminate the protocol amendment information to all participating investigators.

9.2 Data Management Plan

The CRFs will be stored in a locked office in the Nuclear Medicine clinic. Records will be kept using OnCore.

During the clinical investigation, the Protocol Director will evaluate the progress of the trial, including periodic assessments of data quality and timeliness, participant recruitment, accrual and retention, participant risk versus benefit, performance of trial sites, and other factors that can affect study outcome. Monitoring of the trial will occur every 8 weeks and a record of monitoring activities will be maintained by the study team.

The Stanford Cancer Institute Data and Safety Monitoring Committee (DSMC) will audit study related activities to determine whether the study has been conducted in accordance with the protocol, local standard operating procedures, FDA regulations, and Good Clinical Practice (GCP). This may include review of regulatory binders, case report forms, eligibility checklists, and source documents. In addition, the DSMC will regularly review serious adverse events and protocol deviations associated with the research to ensure the protection of human subjects. Results of DSMC audits will be communicated to the IRB and

the appropriate regulatory authorities at the time of continuing review, or in an expedited fashion, as needed.

10. MEASUREMENTS

10.1 Outcome Measures

The principal goal of this study is to compare, in the setting of suspected prostate cancer recurrence, the diagnostic performance of ^{68}Ga -PSMA-11 PET/CT in cases where conventional imaging for detecting recurrent prostate cancer is likely to have false negatives. Sites of suspected disease will be evaluated by ^{68}Ga -PSMA-11 PET/CT and conventional imaging by region for all patients. Specifically, it is hypothesized that the diagnostic performance of the ^{68}Ga -PSMA-11 PET/CT will be superior to anatomical imaging, and that ^{68}Ga -PSMA-11 PET/CT will provide complementary information.

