2. BACKGROUND

2.1 Preliminary information

Data from the American Cancer Society suggests that for 2015 in the United States prostate cancer will continue to be the leading non-cutaneous cancer diagnosis in males with 220,800 estimated new cases, and has the second highest mortality (after lung) with 27,540 estimated deaths (1). Subsequent treatment is multifaceted and may involve observation, surgery (prostatectomy), radiation therapy (external beam or brachytherapy), hormonal therapy, chemotherapy, or a combination of these (2-4).

Up to 40% of the patients with prostate cancer develop biochemical recurrence within 10 years after initial treatment (5). Usually an increase of the PSA-level precedes a clinically detectable recurrence by months to years (6). However, it cannot differentiate between local, regional or systemic disease with the necessary precision that is essential for further disease management (7).

Morphological imaging methods exhibit considerable limitations: sensitivity ranges between 25% and 54% for the detection of local recurrence by transrectal ultrasound (TRUS) or contrast-enhanced CT and is moderately improved by using functional MRI techniques (7-9). The sensitivity for detection of lymph node metastases of CT or MRI is reported to be 30-80% (10). Ultra-small particles of iron oxides (USPIOs) proved to be very effective, but are yet to be approved by regulatory authorities (11). Bone metastases presenting as osteoblastic lesions can be effectively detected by bone scintigraphy, PET, CT and MRI (12, 13).

Various targets have been addressed by molecular imaging to improve the detection of recurrent prostate cancer. PET tracers such as ^{18}F - or ^{11}C -labeled choline and ^{11}C -acetate have been investigated for the diagnosis of recurrent (14-16) prostate cancer. Their feasibility in primary diagnosis is limited because of uptake in benign tissue such as benign prostatic hyperplasia or inflammatory lymph nodes (9, 17). In addition, fluorinated versions are not available in the United States, while ^{11}C -labeled tracers cannot be widely used due to the requirement for an on-site cyclotron due to the short half-life. ^{18}F -FACBC, a new synthetic amino acid, might be superior when compared to ^{11}C -choline PET/CT (18).

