2.5 Study Design

This is a phase 2-3 study with a total of 200 participants with biochemically recurrent prostate cancer. Eligible participants will undergo baseline assessments at enrollment. Study participants will receive ⁶⁸Ga-PSMA-11 and undergo a PET/CT. All patients will first be seen by a Stanford Cancer Institute physician and then referred if appropriate on clinical grounds to Dr [name] or his colleagues for this study. The following steps will take place.

1. After signed the informed consent document, participants will be given a copy of the signed form.
2. Participant will be asked to drink 1 to 2 glasses of water before arrival at the clinic
3. Participants will be weighed and vital signs (heart rate, blood pressure, respiratory rate, pulse oxymetry) will be recorded
4. Study personnel (eg, technologist) will verify subject identify; radiopharmaceutical identity; dose; and administration route. Participant will be injected IV with 3 to 7 mCi of ⁶⁸Ga-PSMA-11
5. A dose of 20 mg of furosemide is recommended to be injected together with, shortly before, or after administration of the radiotracer in order to minimize PET scatter artifacts from excreted radiotracer accumulation in the kidney and urinary bladder that can occur with ⁶⁸Ga-PSMA-11. However, this is not needed if the scanner can reduce such artifacts during image reconstruction
6. Participant will void immediately prior to the scan
7. Approximately 50 to 100 minutes later, a low-dose CT will be obtained from vertex to mid-thighs; this will use 120 kV and dose modulation based on body habitus, ranging 10 to 105 mA. This will be followed by a static PET emission scan over the same area.
8. If participant agrees, immediately after first scan and without reinjecting ⁶⁸Ga-PSMA-11, a second PET/CT will be acquired to compare standard vs digital PET/CT. The CT will be done for attenuation correction only.
9. Vital signs (heart rate, blood pressure, respiratory rate, pulse oxymetry) will be recorded again at the completion of the study.
10. Participants be dismissed.
11. Participants will be contacted at 24 to 72 hours following the scan in order to capture potential late occurring Adverse Events.
12. Clinical follow-up of participant at 3 to 12 months following the scan in order to analyze secondary endpoints.

The ⁶⁸Ga-PSMA-11 PET/CT may be repeated at the completion of treatment to evaluate response to therapy, if requested by the treating physician.

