10.1.1 Primary Outcome

Primary Outcome Title: Confirmation of Prostate Cancer Recurrence

Description: Prostate cancer patients with suspected prostate cancer recurrence will be evaluated with ^{68}Ga -PSMA-11 PET/CT and conventional imaging. The outcome will be reported as the percentage of participants for whom tumor lesions are identified by ^{68}Ga -PSMA-11 PET/CT, and for whom tumor lesions are identified by histopathology/biopsy and/or conventional imaging follow-up. The outcome is reported as percentages without dispersion.

Time Frame: 1 year

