10.1.2 Secondary Outcomes

Secondary Outcome Title: ^{68}Ga -PSMA-11 PET/CT Sensitivity and Specificity by Participant

Description: The sensitivity and specificity of ^{68}Ga -PSMA-11 PET/CT for detection of tumor by participant will be determined, as confirmed by conventional imaging follow-up and/or histopathology/biopsy, within the following 1 year. The sensitivity and specificity of ^{68}Ga -PSMA-11 PET/CT for detection of tumor lesions is reported with the 95% confidence interval.

Time Frame: 12 months

Secondary Outcome Title: ^{68}Ga -PSMA-11 PET/CT Sensitivity and Specificity by Region

Description: The sensitivity and specificity of ^{68}Ga -PSMA-11 PET/CT for tumor detection by location will be determined, as confirmed by conventional imaging follow-up and/or histopathology/biopsy, within the following 1 year. The regions evaluated will be the prostate bed; pelvis outside of prostate bed including lymph nodes; extrapelvic soft tissue; lymph nodes; and organ metastases (non bone); and bone metastases. The

sensitivity and specificity of ^{68}Ga -PSMA-11 PET/CT for detection at the specified tumor locations is reported with the 95% confidence interval.

Time Frame: 12 months

Secondary Outcome Title: ^{68}Ga -PSMA-11 PET/CT Predictive Value by Participant

Description: The predictive value of ^{68}Ga -PSMA-11 PET/CT for detection of tumor, as confirmed by conventional imaging follow-up and/or histopathology/biopsy, within the following 1 year, is assessed by participant. Positive predictive value (PPV) is the probability that participants identified by ^{68}Ga -PSMA-11 PET/CT as having prostate cancer recurrence, do have prostate cancer recurrence. Negative predictive value (NPV) is the probability that participants not identified by ^{68}Ga -PSMA-11 PET/CT as having prostate cancer recurrence, do not have prostate cancer recurrence. The outcome is reported as the PPV and the NPV of ^{68}Ga -PSMA-11 PET/CT for confirmation of prostate cancer recurrence by participant, with 95% confidence interval.

Time Frame: 12 months

Secondary Outcome Title: ^{68}Ga -PSMA-11 PET/CT Predictive Value by Region

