10.3 Primary Endpoint

The primary endpoint is sensitivity and PPV on a per-patient and per-region-basis (Table 1) of ⁶⁸Ga-PSMA-11 PET for detection of tumor location confirmed by histopathology/biopsy.

Table 1: Region Definition

Region	Description
1	Prostate Bed
2	Pelvis outside of prostate bed including lymph nodes
3	Extrapelvic soft tissue, lymph nodes and organ metastases (non-bone)
4	Bone metastases

10.4 Secondary endpoints:

1. PPV and negative predictive value (NPV) on a per-patient and per-region-basis (Table 1) of ⁶⁸Ga-PSMA-11 PET for detection of tumor location confirmed by histopathology/biopsy and conventional imaging follow-up.
2. Sensitivity and specificity on a per-patient basis of ⁶⁸Ga-PSMA-11 PET for detection of tumor location confirmed by histopathology/biopsy and conventional imaging follow-up.
3. Detection rates on a per-patient basis of ⁶⁸Ga-PSMA-11 PET stratified by PSA value in ng/mL (0.2 to < 0.5; 0.5 to < 1.0; 1.0 to < 2.0; 2.0 to < 5.0; ≥ 5.0).

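### Conventional imaging follow-up may alone decide whether a PET result is correct, although the protocol expects it to miss disease, and no rule covers unconfirmed PET-positive findings

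*Combined protocol and SAP*

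**What the plan says.** Section 10.1 places the study in "PET/CT in cases where conventional imaging for detecting recurrent prostate cancer is likely to have false negatives" and hypothesises that PET will outperform anatomical imaging. Section 2.1 gives the background figures: 25% to 54% sensitivity for local recurrence by transrectal ultrasound or contrast-enhanced CT, and, for nodes, "The sensitivity for detection of lymph node metastases of CT or MRI is reported to be 30-80" percent.

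The reference against which PET is judged differs by section:

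- 10.1.1 (primary outcome): participants "for whom tumor lesions are identified by histopathology/biopsy and/or conventional imaging follow-up".
- 10.1.2 (sensitivity, specificity, PPV and NPV): "as confirmed by conventional imaging follow-up and/or histopathology/biopsy, within the following 1 year".
- 10.3 (primary endpoint): sensitivity and PPV of "PET for detection of tumor location confirmed by histopathology/biopsy", with no mention of imaging.
- 10.4 (PPV, NPV, sensitivity and specificity): "confirmed by histopathology/biopsy and conventional imaging follow-up".

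Section 2.5 adds "Clinical follow-up of participant at 3 to 12 months following the scan in order to analyze secondary endpoints". Hypothesis 2 in the synopsis is sensitivity and specificity of at least 70%. Section 11.3.2 plans point estimates and 95% confidence intervals. It does not define a true lesion, a reference-negative case, or the handling of a PET-positive finding that is neither biopsied nor seen on follow-up imaging.

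**The concern.** A test expected to see more than its comparator is being marked by that comparator. Where PET finds real disease that CT or MRI does not show, and nobody biopsies the site, the composite cannot confirm it. If that finding is then counted against PET, better detection lowers PPV and specificity. In the other direction, a man negative on both tests becomes a true negative even if he has disease, which flatters NPV.

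The wording makes this harder to resolve. Under *and/or*, an imaging correlate alone confirms a lesion. Under the *and* of 10.4, read literally, both confirmations are required, so under-confirmation is worse. The same accuracy measures appear under both definitions.

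At stake are the composite-based PPV, specificity and NPV, and the reading of hypothesis 2. Specificity is not part of 10.3, so it has no histology-only version to fall back on. If the scoring rule is chosen after the data are seen, that choice could drive the result.

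**Working it through.** **The plan's own figures.** For a 30% discovery rate in 200 patients, the half-width is 1.96 × √(0.3 × 0.7 / 200) = 0.064, or 6.4 points; the exact interval is 23.7% to 36.9%. The stated 7 points is acceptable. The stated 10 points at 70% needs 0.21 × (1.96 / 0.10)² ≈ 81 reference-positive patients for sensitivity, and as many reference-negative ones for specificity. The plan gives no figure for bias from the reference.

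**Inputs.** From section 2.1, reference sensitivity r = 30%, 54% and 80%. Assumed, not in the documents: prevalence 50%, PET sensitivity 70% and specificity 90%, reference specificity 100%, no biopsies, errors independent given disease, and every unconfirmed PET-positive scored as a false positive.

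**Cells, as fractions of all patients.** Diseased PET-positive 0.5 × 0.7 = 0.35; diseased PET-negative 0.15; disease-free PET-positive 0.05; disease-free PET-negative 0.45. True PPV = 0.35 / 0.40 = 87.5%. True NPV = 0.45 / 0.60 = 75%.

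**Formulas.**
- Apparent PPV = 0.35r / 0.40
- Apparent specificity = [0.45 + 0.15(1 − r)] / [0.5 + 0.5(1 − r)]
- Apparent NPV = [0.45 + 0.15(1 − r)] / 0.60

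| r | PPV (true 87.5%) | Specificity (true 90%) | NPV (true 75%) |
|---|---|---|---|
| 30% | 0.105/0.40 = 26% | 0.555/0.85 = 65% | 92.5% |
| 54% | 0.189/0.40 = 47% | 0.519/0.73 = 71% | 86.5% |
| 80% | 0.280/0.40 = 70% | 0.480/0.60 = 80% | 80% |

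**Other inputs.** Take PET sensitivity and specificity at the 70% of hypothesis 2, with r from 25% to 80%. Apparent specificity is then 60–67% at 30% prevalence, 53–63% at 50% and 40–52% at 80%. Apparent PPV is 13–40% (true 50%), 18–56% (true 70%) and 23–72% (true 90%).

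**With some biopsies.** In the main illustration at r = 30%, suppose 30% of diseased PET-positives are biopsy-proven. Unconfirmed diseased PET-positives are 0.35 × 0.7 × 0.7 = 0.1715. Specificity is 0.555 / (0.5 + 0.1715 + 0.105) = 71%, instead of 65%.

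**If unconfirmed cases are dropped.** At r = 54%, unconfirmed PET-positives are 0.40 − 0.189 = 0.211. With no biopsies, dropping them all leaves 0.189 / 0.189 = 100% PPV against a true 87.5%.

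**If follow-up tracks PET.** Take PET sensitivity and specificity of 70%, prevalence 50%, and follow-up that finds 95% of PET-positive but 10% of PET-negative disease. Apparent specificity is (0.35 + 0.135) / (0.35 + 0.135 + 0.15 + 0.0175) = 74%, above the true 70%. Apparent sensitivity is 0.3325 / (0.3325 + 0.015) = 96%.

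**The case against.** A reader might infer that conventional imaging follow-up is simply the reference standard, that true PET findings are scored as false positives, and that PPV and specificity are therefore bound to be too low. The documents do not support that.

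- The reference in 10.1.1 and 10.1.2 is a composite with histology, and the 10.3 sensitivity and PPV rest on histology alone. This mechanism does not touch them.
- No section says an unconfirmed PET-positive is a false positive. It could equally be called indeterminate or left out.
- The direction can reverse, as the last two calculations show. The plan does not say whether follow-up imaging is read without knowledge of PET.
- The section 2.1 sensitivities are not for follow-up over up to 12 months, when lesions may become visible. Section 2.1 also says functional MRI improves local detection moderately and that osteoblastic bone metastases are well detected; bone is one of the four regions.

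A reader might also infer that hypothesis 2 would fail because of the reference alone. In the main illustration only r = 30% falls below 70%, and with the assumed 30% biopsy confirmation it does not. Section 11.3.2 sets no pass/fail test.

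These objections stand as limits on size and direction, but they do not remove the conflict between sections or the missing rule. Nor can follow-up be assumed to resolve the issue. The pilot men in section 2.1 were untreated with rising PSA, 5 to 75 months from recurrence, and their conventional imaging was still non-contributory. Section 2.5 also foresees treatment after the scan, which could keep lesions from appearing.

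**Conclusion.** The point holds in limited form and should be fixed. A modality that the protocol expects to miss disease can alone set disease status for the 10.1.1 primary outcome and the 10.1.2 accuracy measures, and 10.1, 10.3 and 10.4 give three different references. If unconfirmed PET-positives count as false, composite PPV falls, and so does specificity when errors are independent. In the main illustration specificity loses 10 to 25 points, against a planned precision of about 10. Those figures rest on assumed prevalence and PET accuracy, no biopsies, and background sensitivities applied to follow-up imaging; they show possible size and are not estimates. Biopsy confirmation or lesions emerging during follow-up reduce the bias, and some handling rules reverse it. The histology-only endpoint in 10.3 is unaffected.

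**What to change.** 1. Use one composite in 10.1.1, 10.1.2 and 10.4: reference-positive means positive histology or a correlate on follow-up imaging, with histology overriding imaging for the same site. State how this relates to the histology-only endpoint in 10.3.
2. Define three classes per patient and per region: reference-positive; reference-negative, including PET-negative cases with negative follow-up and no biopsy; and unconfirmed, meaning PET-positive with negative follow-up imaging and no histology.
3. Report composite PPV and specificity with bounds: all unconfirmed false, and all unconfirmed true. Do not make the estimate that excludes unconfirmed cases the headline, because it can push PPV up.
4. Report histology-verified and imaging-verified results separately, and state that specificity and NPV also depend on disease missed by both tests.

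The cost is wording and an extra table column, with no extra procedures. The result is a range instead of one number, and it may be wide: in the illustration at r = 54% with no biopsies, PPV runs from 47% to 100%. Any histology obtained narrows it.

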10.1.1 Primary Outcome

Primary Outcome Title: Confirmation of Prostate Cancer Recurrence

Description: Prostate cancer patients with suspected prostate cancer recurrence will be evaluated with ^{68}Ga -PSMA-11 PET/CT and conventional imaging. The outcome will be reported as the percentage of participants for whom tumor lesions are identified by ^{68}Ga -PSMA-11 PET/CT, and for whom tumor lesions are identified by histopathology/biopsy and/or conventional imaging follow-up. The outcome is reported as percentages without dispersion.

Time Frame: 1 year

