INVESTIGATIONAL PRODUCT	⁶⁸ Ga-PSMA-11; also known as: 
 • DFKZ-11 • HBED-CC PSMA • The “Heidelberg compound”
PRIMARY OBJECTIVE	To evaluate ⁶⁸ Ga-PSMA-11 PET/CT for detection of recurrent prostate cancer after initial therapy in patients with elevated PSA
SAMPLE SIZE	200 participants
GOALS	
Prospective single-center, single-arm study.
 
HYPOTHESES
 
 1. At least 30% of these patients will have one or more lesions detected on ⁶⁸Ga-PSMA-11 PET/CT. 2. ⁶⁸Ga-PSMA-11 PET/CT will have sensitivity and specificity of at least 70% in this context. 
STATISTICAL TEST
 
We will calculate point estimates and 95% confidence intervals for:
 
 1. Percentage of patients who had true lesions. 2. Sensitivity and specificity of ⁶⁸Ga-PSMA-11 PET/CT. 
STATISTICAL POWER AND SAMPLE SIZE
 
We expect to recruit 200 patients over the course of this trial. The number of lesions cannot be predicted at this time, however, if our expectation of a 30% discovery rate is correct, the resulting confidence interval would be roughly +/- 7 percentage points, and confidence intervals for specificity/sensitivity would be roughly +/- 10 percentage points.

SCHEMA

Eligible participant with prostate cancer

LIST OF ABBREVIATIONS AND DEFINITION OF TERMS

Ga-68; ^{68}Ga	Gallium-68
IRB	Institutional Review Board
IV	Intravenous
MRI	Magnetic resonance imaging
NPV	Negative predictive value
PPV	Positive predictive value
PET	Positron emission tomography
SUV	Standardized Uptake Value
PSMA	Prostate Specific Membrane Antigen

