11.4 Sample Size

We expect to recruit 200 patients over the course of this trial. The number of lesions cannot be predicted at this time, however, if our expectation of a 30% discovery rate is correct, the resulting confidence interval would be roughly ± 7 percentage points, and confidence intervals for specificity/sensitivity would be roughly ± 10 percentage points.

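### The per-participant outcomes in 10.1 do not require PET and the reference standard to agree on region, while 10.3 and 10.4 refer to tumor location without a matching rule

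*Combined protocol and SAP*

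**What the plan says.** **Section 10.1.1 (Primary Outcome)** reports the percentage of participants for whom PET identifies tumor "and for whom tumor lesions are identified by histopathology/biopsy and/or conventional imaging follow-up", with a one-year time frame. Both conditions apply to the man. Neither refers to the site of the other.

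**Section 10.1.2 (Secondary Outcomes)** defines participant-level PPV as the probability that men identified by PET "as having prostate cancer recurrence, do have prostate cancer recurrence". Confirmation may come from conventional imaging follow-up and/or histopathology within the following year. Participant-level sensitivity and specificity are listed apart from the by-region versions.

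**Section 10.3 (Primary Endpoint)** names sensitivity and PPV, per patient and per region, of "PET for detection of tumor location confirmed by histopathology/biopsy". Section 10.4 uses the same location language for its PPV, NPV, sensitivity and specificity endpoints and adds conventional imaging follow-up to the reference standard. Table 1 defines four regions.

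**Section 11.3.2 (Analysis Plan)** estimates the percentage of patients with true lesions but does not say what makes a lesion true.

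No section says how to score a man whose PET lesion lies in one region and whose confirmed tumor lies only in another.

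**The concern.** Every participant enters with biochemical recurrence, and confirmation stays open for a year. Disease that PET missed can become visible during that year and, under the literal 10.1 wording, validate an unrelated PET focus in the same man.

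That matters here because the case for the scan is localisation. Section 2.1 says of PSA that "it cannot differentiate between local, regional or systemic disease with the necessary precision that is essential for further disease management". A wrong-site call scored as a success is the kind of error a localisation study should be able to show.

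The per-patient results are also set against a stated hypothesis, that "PET/CT will have sensitivity and specificity of at least 70% in this context". If the scoring rule is left open, two analysts could classify the same man differently after the data are in, and one of the two choices is systematically the more favourable.

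**Working it through.** **The plan's own precision figure.** Section 11.4 states: "We expect to recruit 200 patients over the course of this trial". It adds that "if our expectation of a 30% discovery rate is correct, the resulting confidence interval would be roughly ± 7 percentage points". The Wald half-width is 1.96 × √(0.30 × 0.70 / 200) = 0.064, or 6.4 points. The Clopper-Pearson interval for 60/200 is 23.7% to 36.9%. The stated figure is reproduced. The plan also says "confidence intervals for specificity/sensitivity would be roughly ± 10 percentage points". At 70% this needs (1.96/0.10)² × 0.70 × 0.30 ≈ 81 men in the denominator, a number the plan does not state. A matching rule changes neither the 200 nor these formulas.

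**One man under each definition.** Suppose PET is positive in region 1 only, region 1 is not confirmed, and tumor is confirmed in region 4 only, within the year.

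| Definition | How he is scored |
|---|---|
| 10.1.1, read as a joint condition | Confirmed |
| 10.1.2, PPV by participant | True positive |
| 10.1.2, sensitivity by participant | Detected, if read literally; no site condition |
| 10.1.2, by region | False positive in region 1, false negative in region 4 |
| 10.3 and 10.4, per patient | Location language suggests not confirmed; no rule given |
| 11.3.2 | Undefined |

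**Direction.** Let T be the any-location hits, k ≥ 0 those confirmed only in PET-negative regions, P the PET-positive men and D the reference-positive men. P, D and the 200 are the same under both rules.

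- Confirmed rate: (T − k)/200 against T/200.
- PPV: (T − k)/P against T/P.
- Sensitivity: (T − k)/D against T/D.

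All three are lower under matching, or equal if k = 0. With f = k/T, each matched value is the any-location value × (1 − f). The discordant man is PET-positive and reference-positive, so NPV and specificity do not change.

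**Illustrative size.** The documents give no value for f. For an any-location sensitivity of 70%, f = 5%, 10% and 20% give 70 × 0.95 = 66.5%, 70 × 0.90 = 63% and 70 × 0.80 = 56%.

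As a second illustration, apply the plan's 30% to the confirmed rate (T = 60 of 200) and assume P = 75 and D = 86:

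| f | k | Confirmed rate | PPV | Sensitivity |
|---|---|---|---|---|
| 0% | 0 | 30.0% | 80% | 69.8% |
| 5% | 3 | 28.5% | 76% | 66.3% |
| 10% | 6 | 27.0% | 72% | 62.8% |
| 20% | 12 | 24.0% | 64% | 55.8% |

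With D = 81 instead, sensitivity runs 74.1%, 70.4%, 66.7% and 59.3%. Whether a given f takes the result below 70% therefore depends on where it starts.

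**The case against.** The strongest reply is that the plan never adopts an any-location rule. Sections 10.3 and 10.4 speak of tumor location, and 11.3.2 of true lesions, and both lean towards matching. The PPV wording in 10.1.2 is weak evidence that location was excluded on purpose, because the by-region outcome reuses the same generic NPV phrase. This stands. A reader might infer that the trial has chosen to credit any recurrence anywhere in the man; the documents do not support that. What they show is a literal wording in 10.1 and a different emphasis in 10.3 and 10.4, with no rule in either.

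Second, 10.1.1 can be read as two separate percentages, one for PET and one for the reference standard, with no joint hit. That reading is possible, though the outcome's title, which speaks of confirming recurrence, fits it poorly. It leaves the PPV and sensitivity in 10.1.2 without a site condition.

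Third, location is measured. Section 10.1 has sites evaluated by region in all patients, and the by-region outcomes would expose a mismatch between regions. This is true, so it cannot be said that the trial ignores location. But those outcomes do not correct the per-participant figures.

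Fourth, the follow-up year does not work only in PET's favour. It also turns PET-negative men into false negatives, which lowers sensitivity and NPV. The claim here is only relative to a matched rule over the same follow-up. In addition, 10.3 accepts histopathology alone, so a metastasis seen only on follow-up imaging would not count there.

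**Conclusion.** The concern holds as a conflict between definitions with a known direction and an unknown size. Followed literally, 10.1.1 (as a joint condition) and the participant-level PPV in 10.1.2 count a wrong-site PET finding plus tumor confirmed elsewhere within a year as a success. Compared with a region-matched rule, that can only raise the confirmed rate, PPV and sensitivity, or leave them equal.

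A reader might go on to infer from the illustrations that the trial would miss its 70% sensitivity by 3.5 to 14 points. The documents do not support that. Those figures assume a start at exactly 70% and a wrong-site share of 5% to 20%, neither of which the plan gives, and the loss is zero if no such man occurs. Nor is the 70% tied to a test or decision rule: 11.3.2 plans estimates and confidence intervals only.

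The point is still more than a missing detail. The literal 10.1 wording is never less favourable than the location-based reading of 10.3 and 10.4, and the choice should not be left until the results are known.

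**What to change.** State one rule in 10.1.1, 10.1.2, 10.3 and 10.4, using the Table 1 regions:

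- A participant is a true positive only if at least one region is positive on PET and confirmed positive by the reference standard in that same region.
- A man whose PET-positive regions are all unconfirmed, and whose tumor is confirmed only in PET-negative regions, stays in the PPV denominator as not confirmed and in the sensitivity denominator as not detected. Being reference-positive, he does not enter specificity.
- Any-location figures are reported alongside as supportive, with the number of discordant men.

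Say in 10.1.1 whether one joint percentage or two separate ones are meant, and define a true lesion in 11.3.2 by the same rule. Note as a limitation that region matching still scores a mismatch within one region, such as two different bones in region 4, as a hit.

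The cost is a few sentences. Section 10.1 already has sites evaluated by region in all patients, so no new imaging is needed; the region of each biopsy has to be on record. The downside is that the per-patient figures may be somewhat less favourable.
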